6.3.2 Blinding and Code-breaking Procedures

With the exception of the Booster Arms in Supplemental Cohort 1 and the Comparator Arm common to Supplemental Cohorts 1 and 2, the study will be performed in a modified double-blind (observer-blind) fashion:

- Investigators and study staff who conduct the safety assessment and monitoring and the participant will not know which vaccine is administered in order to decrease the risk of potential bias. Study site staff who administer the vaccine may also be blinded if they are not involved in preparation of the vaccine.
- Only the study-site staff who prepare the vaccine and are not involved with the safety evaluation will know which vaccine is administered
- Testing laboratories will be blinded

At the time of the interim analysis (see [Section 9.5](#)) of the Original Phase II Cohort, unblinding at the group-level occurred to inform Sponsor decision on dose-selection and progression to Phase III. Individual level code will be maintained by the Independent unblinded statistical group till the end of the study. In addition to that, Global Clinical Immunology (GCI) and other laboratories undertaking assays for the study will be kept blinded until all test results are released.

The code may be broken in the event of an AE only when the identification of the vaccine received could influence the treatment of the participant. Code-breaking should be limited to the participant(s) experiencing the AE.

The blind can be broken by the Investigator or a delegate through the IRT system, as explained in the code-breaking procedures described in the Operating Guidelines. Once the emergency has been addressed by the site, the Investigator or a delegate must notify the Sanofi Pasteur Responsible Medical Officer (RMO) if a participant's code was broken. All contact attempts with the Sponsor prior to unblinding are to be documented in the source documents, and the code-breaking CRF is to be completed.

The Independent Ethics Committee / Institutional Review Board (IEC / IRB) must be notified of the code-breaking, in accordance with local regulations. All documentation pertaining to the event must be retained in the site's study records and in the Sanofi Pasteur files. Any intentional or unintentional code-breaking must be reported, documented, and explained, and the name of the person who requested it must be provided to the Sponsor.

A request for the code to be broken may also be made:

- by the Global Pharmacovigilance (GPV) Department through an internal system for reporting to Health Authorities in the case of an unexpected SAE considered causally related, as described in International Council for Harmonisation (ICH)^a E2A. In this case, the code will be broken only for the participant(s) in question. The information resulting from code-breaking (ie, the participant's study intervention or group assignment) will not be communicated to either the Investigator or the immediate team working on the study, except for the GPV representative.

The code-breaking procedures are described in the Operating Guidelines.

6.4 Study Intervention Compliance

The following measures will ensure that the study intervention is administered as planned (see [Table 6.1](#)), and that any non-compliance is documented so that it can be accounted for in the data analyses:

- All study interventions will be administered by qualified and trained study personnel
- The person in charge of study intervention management at the site will maintain accountability records of study intervention delivery to the study site, study intervention inventory at the site, dose(s) given to each participant, and unused or wasted doses

6.5 Dose Modifications

Not applicable

6.6 Access to Authorized/Approved vaccine during the study

If an approved/authorized vaccine is available in the country or region where the study is conducted, Investigators will discuss this information with prospective study participants who have not yet received an authorized/approved vaccine at the time of informed consent and who will be encouraged to obtain the approved/authorized vaccine if applicable to them. Recruitment of eligible participants into one of the study cohorts evaluating priming vaccines (Original Phase II Cohort and the Supplemental Cohorts Comparator Group) will proceed only if, despite encouragement, the candidate participant expresses no intention to seek an authorized or approved vaccine at least until completion of the key follow-up timepoint (D43 for the study cohorts evaluating priming vaccines) for informing either progression to Phase III and dose selection (for Original Phase II Cohort participants) or suitability of variant-containing vaccines for authorization/approval (for the Supplemental Cohorts Comparator Group)

If the participant is enrolled and seeks vaccination of an authorized/approved vaccine outside of the study, he/she will be encouraged to discuss this intention proactively with the study Investigator and will be permitted to receive the authorized vaccine at any time. If the participant receives the authorized/approved vaccine, this information would be collected and the

^a All unexpected and related SAEs submitted to European Union competent authorities must be unblinded.

participant's data up to the point of receipt of authorized/approved vaccine will be included in the primary analysis for immunogenicity and safety. Participants will continue to be followed for the duration of the study as per scheduled visits and procedures. Participants in the cohorts evaluating priming vaccines will not receive the second vaccination if they have received the authorized/approved vaccine between the first and second scheduled vaccination.

6.7 Continued Access to Study Intervention After the End of the Study

In the event that the vaccine formulation evaluated in this study is deemed safe and effective by regulatory authorities, this authorized/approved vaccine may be offered to eligible participants in this study who received a formulation considered less effective to that authorized by the regulatory authorities, if permitted by local regulations and in alignment with local recommendations.

6.8 Treatment of Overdose

Since the study intervention is administered by a health care professional, it is unlikely that overdose by injection occurs.

However, in the event of an overdose, the Investigator should:

- 1) Contact the RMO immediately.
- 2) Evaluate the participant to determine, in consultation with the RMO, whether study intervention should be interrupted.
- 3) Closely monitor the participant for any AE/SAE.
- 4) Document the quantity of the excess of the overdose in the source documents.

6.9 Concomitant Therapy

At the time of enrollment, all ongoing medications and other therapies (eg, some vaccines, immunoglobulins and monoclonal antibodies) should be recorded in the source document.

Documentation in the CRF of ongoing concomitant medication(s) will be limited to specific categories of medication(s) of interest beginning on the day of first vaccination.

Reportable medications/vaccinations will be collected in the CRF from the day of each study vaccination to the end of the solicited and unsolicited follow-up period after each study vaccination in all participants, with the exception of influenza and COVID-19 vaccination which will be collected throughout the study in all participants. In addition, any medications used for COVID-19 prophylaxis (eg, SARS-CoV-2 antivirals, monoclonal or polyclonal antibodies or plasma) will be collected throughout the study in all participants.

Reportable medications include medications that impact or may impact the consistency of the safety information collected after any vaccination and/or the immune response to vaccination.

The following reportable medications are defined:

- Category 1: medications impacting or that may have an impact on the evaluation of the safety (eg, antipyretics, analgesics, and non-steroidal anti-inflammatory drugs [NSAIDs],

anticoagulants, antithrombotics) Note: Topical analgesics should NOT be applied at the injection site of study intervention; however, if they are applied inadvertently, they should be recorded.

- Category 2: medications impacting or that may have an impact on the immune response (eg, hydroxychloroquine, other vaccines, blood products, immunoglobulins, monoclonal antibodies, convalescent plasma, antivirals and antiretrovirals, immune-suppressors, immune-modulators with immunosuppressive properties, anti-proliferative drugs such as DNA synthesis inhibitors)
- Category 3: medications impacting or that may have an impact on both the safety and the immune response (eg, systemic steroids/corticosteroids)

In addition to the above, some therapies or vaccines are to be collected even if they were taken before study vaccination or are stopped prior to enrollment, or if they are taken after the solicited period and at any time during the study. In this regard, information on use of influenza vaccines in the 6 months prior to enrollment is to be collected; information on immunoglobulins, plasma and other blood products, monoclonal antibodies, antineoplastics, immunomodulators (including high-dose corticosteroids utilized for more than 10 days) administered up to 90 days before vaccination will be collected.

Dosage and administration route, homeopathic medication, inhaled steroids, as well as topical treatments, ophthalmic and ear treatments will not be recorded (except topical analgesics applied at the injection site of study intervention).

Medications given in response to an AE will be captured in the “Action Taken” section only. Medications administered during a COVID-19-like illness episode will be captured in the appropriate CRF and will not be considered as concomitant medications. Medications will not be coded. No details will be recorded in the concomitant medication Form of the CRF unless the medication(s) received belongs to one of the pre-listed categories.

6.9.1 Rescue Medicine

Appropriate medical equipment and emergency medications, including epinephrine (1:1000), must be available at the study site in the event of an anaphylactic, vasovagal, or other immediate allergic reaction.

7 Discontinuation of Study Intervention and Participant Discontinuation/Withdrawal

7.1 Discontinuation of Study Intervention

7.1.1 Temporary Contraindications

Should a participant^a experience one of the conditions listed below, the Investigator will postpone further vaccination (if applicable, ie, for groups evaluating priming vaccine candidates) until the condition is resolved.

- TCI01: Febrile illness (temperature $\geq 38.0^{\circ}\text{C}$ [$\geq 100.4^{\circ}\text{F}$]) or moderate or severe acute illness / infection on the day of vaccination, according to Investigator judgment
- TCI02: Receipt of any vaccine (other than the study vaccine) in the 30 days prior to the first study vaccination except for influenza vaccine which may be received at any time with respect to study intervention
- TCI03: Receipt of any vaccine (other than the study vaccine[s]) in the 21 days preceding or on the day of the second study vaccination or planned receipt of any vaccine in the 30 days following the second study vaccination except for influenza vaccine, which may be received at any time with respect to study intervention.

7.1.2 Definitive Contraindications

Participants will permanently discontinue (definitive discontinuation) study intervention (if applicable, ie, for groups evaluating priming vaccine candidates) for the reasons listed below. These participants must not receive any additional dose of study intervention but should continue to be followed for safety and other study assessments/procedures. Additional unscheduled visits may be performed for safety reasons and information will be reported in the source documents.

Should a participant experience 1 of the conditions listed below, the Investigator will discontinue vaccination:

- DCI01: Pregnancy, as indicated by a positive urine or serum test
- DCI02: An anaphylactic or other significant allergic reaction to the previous dose of vaccine
- DCI03: AE assessed as related to the study vaccine following the previous dose of vaccine which may place the participant at unreasonable or significant risk of injury or illness following repeat exposure to study vaccine, based on Investigator's judgment
- DCI04: Positive NAAT at V01 or symptomatic COVID-19 or asymptomatic SARS-CoV-2 infection confirmed by NAAT after V01 and before V02
- DCI05: Receipt of COVID-19 vaccine (other than the study vaccine) or anti-SARS-CoV-2 monoclonal or polyclonal antibody in the period between the first study vaccination and the day corresponding to the second study vaccination.

^a Applies to the Primary Series only

If the participant is enrolled and seeks vaccination of an authorized/approved vaccine outside of the study, he/she will be encouraged to discuss this intention proactively with the study Investigator and will be permitted to receive the authorized vaccine at any time. If the participant receives the authorized/approved vaccine, this information would be collected and the participant's data up to the point of receipt of authorized/approved vaccine will be included in the primary analysis for immunogenicity and safety. Participants will be invited to a visit prior to receiving the vaccine and invited to provide a blood sample for immunological assessment. If the visit occurs more than 1 month after the D134 visit for the groups evaluating priming vaccine candidates (Original Phase II Cohort Arms and the Comparator Arm for the Supplemental Cohorts) or more than 1 month after D91 visit for groups evaluating booster vaccine candidates (Booster Arms in Supplemental Cohorts 1 and 2), a PBMC sample will also be collected if the participant is in the cellular immunity and mucosal subset instead of the D366 sample. Participants will continue to be followed for the duration of the study as per scheduled visits and procedures except for receipt of the second vaccination as detailed above.

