5.1 Inclusion Criteria

Participants are eligible for the study only if all of the following criteria are met:

I01: Aged 18 years or older on the day of inclusion^a

I02: A female participant is eligible to participate if she is not pregnant or breastfeeding and one of the following conditions applies:

- Is of non-childbearing potential. To be considered of non-childbearing potential, a female must be post-menopausal for at least 1 year or surgically sterile.

OR

- Is of childbearing potential and agrees to use an effective contraceptive method or abstinence from at least 4 weeks prior to the first vaccination until at least 12 weeks after the last vaccination (ie, second dose of primary series or booster injection).
- A participant of childbearing potential must have a negative highly sensitive pregnancy test (urine or serum as required by local regulation) within 4 hours before any dose of study intervention, see [Section 8.4.5](#) (pregnancy testing).

I03: Informed consent form has been signed and dated

I04: Able to attend all scheduled visits and to comply with all study procedures

I05: Covered by health insurance, only if required by local, regional, or national regulations

I06: SARS-CoV-2 rapid serodiagnostic test performed at the time of enrollment to detect presence of SARS-CoV-2 antibodies (Original Phase II Cohort)

^a Participants in the Comparator Group for Supplemental Cohorts 1 and 2 must be 18 to 55 years of age.

I07: For persons living with human immunodeficiency virus (HIV), stable HIV infection determined by participant currently on ARVs with CD4 count > 200/mm³

I08: Does not intend to receive an authorized/approved COVID-19 vaccine from first vaccination to 3 weeks after the second vaccination (D43) despite encouragement by the Investigator to receive the authorized vaccine available to them at the time of enrollment^a

I09: Supplemental cohorts: for participants originally enrolled in the Phase II Cohort of the study, informed consent has to be signed and dated for transitioning to Supplemental Cohort 2

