8.1.4 Clinical Safety Laboratory Assessments

Urine or serum pregnancy testing will be performed in females of childbearing potential before each vaccination.

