- The Investigator should promptly inform the Sponsor and will record pregnancy information together with the contraceptive method on the appropriate form and submit it to the Sponsor no later than 1 month of learning of the pregnancy. Pregnancy status will be collected, follow-up of the participant will continue as part of the study, but the participant will not be followed-up until the pregnancy outcome and the offspring will not be followed.
- Any post-study pregnancy-related SAE considered reasonably related to the study intervention by the Investigator will be reported to the Sponsor as described in [Section 8.4.4](#). While the Investigator is not obligated to actively seek this information in former study participants, he or she may learn of an SAE through spontaneous reporting.
- Any female participant who becomes pregnant while participating in the study will discontinue study intervention until delivery or until delivery and end of lactation. However, the participant will be followed for safety assessment (and may be followed for immunogenicity assessment, if applicable).

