10.2 Appendix: Clinical Laboratory Tests

A urine or serum human chorionic gonadotropin (hCG) pregnancy test (as needed for females of childbearing potential) will be performed before each vaccination.

- The tests detailed in [Table 10.1](#) will be performed by the site-selected local laboratory.
- Protocol-specific requirements for inclusion or exclusion of participants are detailed in [Section 5](#) of the protocol.
- Additional tests may be performed at any time during the study as determined necessary by the Investigator or required by local regulations.

Table 10.1: Protocol-required laboratory tests

Laboratory Tests	Time period for assessment	Parameters
Screening Tests	pre-injections 1 and 2 at D01 and V02 (D22*), respectively	Highly sensitive urine or serum human chorionic gonadotropin (hCG) pregnancy test (as needed for females of childbearing potential**)
	D01	Rapid diagnostic testing for SARS-CoV2 antibody screening

* For SARS-CoV-2-naïve participants only

** To be considered of non-childbearing potential, a female must be post-menopausal for at least 1 year or surgically sterile

Participants, outcome assessors, Investigators, laboratory personnel, Sponsor study staff, and those administering the study intervention if not involved in preparing the study intervention will be blinded to Intervention Group; and those preparing/administering the study interventions will be unblinded.

Laboratory results that could unblind the study will not be reported to investigative sites or other blinded personnel until the study has been unblinded.

10.3 Appendix: AEs and SAEs: Definitions and Procedures for Recording, Evaluating, Follow-up, and Reporting

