- In case of pregnancy during the primary series and if at least 1 dose of the study vaccine(s) has been administered, the participant will not be discontinued from the study, but no further vaccination will be administered until after she is no longer pregnant (if applicable). However, the participant will be followed for safety assessment (and may be followed for immunogenicity assessment, if applicable).

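### Section 7.1.2 bars any further dose permanently after a pregnancy, while Appendix 10.4 only defers it; the Table 10.1 footnote on the D22 pregnancy test also conflicts with the rest of the protocol

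*Protocol*

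**What the plan says.** **Further doses after a pregnancy**

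- Section 7.1.2 applies to groups evaluating priming vaccine candidates. It opens with "Participants will permanently discontinue (definitive discontinuation) study intervention" and adds "These participants must not receive any additional dose of study intervention". The first item on its list is "DCI01: Pregnancy, as indicated by a positive urine or serum test". Section 7.1.1 holds a separate list of conditions for which vaccination is merely postponed, and pregnancy is not on it.
- Appendix 10.4 addresses pregnancy during the primary series once at least one dose has been given. It states that "no further vaccination will be administered until after she is no longer pregnant (if applicable").
- Section 8.4.5 says that any female participant who becomes pregnant during the study "will discontinue study intervention until delivery or until delivery and end of lactation". This bullet sits under the heading for pregnancies that start after the contraception or abstinence period, which runs to 12 weeks after the last vaccination.

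**Pregnancy testing before the second injection**

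- I02 in Section 5.1 requires a negative test "within 4 hours before any dose of study intervention".
- Section 8.1.4 states: "Urine or serum pregnancy testing will be performed in females of childbearing potential before each vaccination".
- The Comparator Group schedule (Table 1.3) marks the test at both V01 and V02, and its footnote sets no limit by naïve status.
- The opening sentence of Appendix 10.2 likewise calls for a test before each vaccination.
- The footnote attached to D22 in Table 10.1, in that same appendix, reads "For SARS-CoV-2-naïve participants only".

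**The concern.** Sections 7.1.2 and 10.4 speak to the same woman, one who is in a two-dose series, has received the first dose and has become pregnant. Read alone, the first says she is never dosed again and the second says she waits. Whether she is re-exposed to the study vaccine should not depend on which section the site consults. The analysis plan cannot repair this, because it is an instruction to sites.

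The testing footnote raises a smaller question of the same kind. Section 9.3 defines a category of Comparator Group participants who are non-naïve at second injection. Taken literally, the footnote leaves those women out of a test that four other places require.

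**Working it through.** No figure is at stake, so the check is a comparison of the instructions.

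**1. Do Sections 7.1.2 and 10.4 cover the same case?** Yes. Section 7.1.2 is limited to the priming groups and concerns doses still to come. Appendix 10.4 is limited to the primary series after at least one dose. Two outcomes show how they differ:

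- *Positive test at V02, still pregnant.* No dose is given at that visit under either section. Afterwards, Section 7.1.2 allows none ever, while Appendix 10.4 lifts the restriction once the pregnancy is over.
- *Positive test after dose 1, with the pregnancy ending early.* Section 7.1.2 still bars the dose, because its trigger is the positive test. Appendix 10.4 permits it. Appendix 10.4 itself anticipates early pregnancy loss. Tests are scheduled only at V01 and V02, so reaching this outcome before V02 would need an unscheduled positive test.

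**2. Where does Section 8.4.5 fit?** Dose 2 is due 21 days after V01 with a window of +3 days, so by day 24 after dose 1. The contraception period runs at least 12 weeks, or 12 × 7 = 84 days, after the last vaccination. A pregnancy under the heading where the bullet sits therefore starts at least 84 − 24 = 60 days after the dose 2 window has closed, counting from dose 1. Read by its placement, the bullet does not compete for a pending dose 2. Read by its wording, which covers any female participant, it gives a third end-point, and itself offers two alternatives without saying which applies. For a pregnancy that ends without delivery, its condition is never met.

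**3. What does the per-protocol definition (Section 9.3) do with each choice?**

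- Following Section 7.1.2, she receives one injection and is excluded for not having received both.
- Following Appendix 10.4, she receives the second injection despite a definitive contraindication and is excluded on that criterion. A late dose would also miss the time window.

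She leaves the per-protocol set either way. Full analysis set membership needs only one study injection, so it does not depend on the choice either.

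**4. Who falls outside the footnote?** For the Comparator Group, non-naïve at second injection means anti-S positive on D01, or NAAT positive on D01 or D22. DCI04 already stops dose 2 for a positive NAAT at V01, or for infection confirmed by NAAT between V01 and V02. It does not mention anti-S positivity. Enrolment rests on a negative on-site rapid test, while Sections 8.1.5 and 8.1.5.2 classify naïve status from other assays. A rapid-test-negative, anti-S-positive woman could therefore reach V02 and be outside the footnote, though I02, Section 8.1.4, Table 1.3 and the opening of Appendix 10.2 all require her to be tested.

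**The case against.** The strongest reply is that Section 7.1.2 governs in practice. Table 1.3 has a V02 row for temporary and definitive contraindications, which leads the site to Section 7.1, where pregnancy appears only on the definitive list. Appendix 10.4 is about collecting pregnancy information, and its sentence is qualified by the words on applicability. This makes the permanent bar the likelier rule at the visit. It does not remove the conflict, because the protocol nowhere ranks the two sections and the appendix sentence is a direct instruction on vaccination.

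Three stronger readings might be inferred, and the documents do not support them:

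- *Three fully competing rules for the D22 dose.* The heading above the Section 8.4.5 bullet places it after the contraception period, when dose 2 would not normally be pending. Nor can lactation after a pregnancy that begins following a negative D01 test arise by D22.
- *Women are likely to receive dose 2 untested.* That would mean disregarding four direct instructions. The footnote also reads plausibly as a label for the two-dose group, which the protocol repeatedly calls SARS-CoV-2-naïve and unvaccinated. Booster arms have no second injection.
- *The analysis sets are distorted.* Membership of the per-protocol and full analysis sets is the same whichever rule is followed.

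**Conclusion.** The conflict between Section 7.1.2 and Appendix 10.4 is real: a permanent bar in one and a deferral in the other for the same situation, with the deferred dose listed as a per-protocol exclusion. The Section 8.4.5 wording adds to the confusion but, given its placement, is secondary. The Table 10.1 footnote contradicts four other instructions as written, and is most likely an unclear group label.

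The size is small. The Original Phase II Cohort's dosing is described as past, so exposure is in practice confined to the Comparator Group, planned at 515 and all aged 18-55. The protocol gives neither the number of women of childbearing potential nor the number of pregnancies expected between D01 and D22; few are assumed. The consequence is consistency of a dosing and safety instruction across sites. No effect on power or on the primary analysis is claimed.

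**What to change.** Reconcile Sections 7.1.2, 10.4 and 8.4.5 to one rule on further doses after a pregnancy, chosen by the sponsor's medical team and worded identically in all three. If the Section 8.4.5 bullet is meant only for pregnancies after the contraception period, its wording should say so. This review does not say which rule is right.

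Reconcile the Table 10.1 footnote with I02, Section 8.1.4, the schedules of activities and the opening of Appendix 10.2, so that one statement says who is tested before each injection. If the footnote is only a group label, name the group.

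The cost is text alignment in four places. The V02 test is already scheduled, so no procedure is added.
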